### **Permitted dose adjustments and interruptions of study treatment**

For patients who are unable to tolerate the protocol-specified dosing scheme, dose adjustments and interruptions are permitted to allow the patient to continue on study drug. In general, in a first attempt to treat patients who have difficulties to tolerate their immunosuppressive regimen, symptomatic treatment should be considered. The following guidelines should be followed.

### **Everolimus**

The recommended route of administration for everolimus is orally, therefore patients who are unable to take oral medications by 1 month post transplant will be excluded from the study.

For patients for patients who are unable to tolerate the protocol-specified dosing scheme due to a decrease in the platelet count, a decrease in hemoglobin level, a decrease in white blood count, an increase in cholesterol level, an increase in triglyceride level, or

other adverse events, dose adjustments are permitted in order to keep the patient on the study drug.

The everolimus dose should be decreased by at least one third of the total daily dose of the study if a dose reduction is necessary. The everolimus C-0h blood trough level should still be kept  $\geq 3$  ng/mL. Everolimus should be discontinued if a C-0h blood trough level  $\geq 3$  ng/mL cannot be maintained due to toxicity or intolerable side-effects. The total daily dose should be adjusted by increasing or decreasing the dose depending on the C-0h blood trough level. If the C-0h blood trough level is  $< 3$  ng/mL, everolimus will be increased by doubling the dose and if the C-0h blood trough level is  $> 8$  ng/mL, the everolimus dose will be decreased by at least by 25 % of the daily dose. Interruption of study drug and/or temporarily everolimus C-0h blood trough level  $< 3$  ng/mL are up to the discretion of the investigator and the investigator has to assure for adequate immunosuppression, i.e. by compensating interruption and/or temporarily everolimus C-0h blood trough level  $< 3$  ng/mL by the temporary introduction of a higher exposure of tacrolimus.

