## **Study Population**

The study population will consist of adult (age >18 years) male and female primary liver transplant recipients. All patients will have received a liver allograft from a deceased donor.

It is anticipated our center will need to screen approximately 140 male and female adult liver transplant recipients. Of these 140 liver allograft recipients, it is expected a minimum of 90 will fulfill the inclusion and none of the exclusion criteria at baseline and will be able to be randomized in a 2:2:1 manner to receive one of the three proposed immunosuppressive regimens.

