## **Inclusion Criteria at Baseline**

Patients eligible for inclusion in this study have to fulfill all of the following criteria:

1. A signed informed consent prior to patient participation in the study and before any assessment is performed.
2. Patients who are able to take oral medication at 1 month post transplant

3.  $\geq 18$  years old
4. Undergoing first OLT
5. Dialysis for 45 days or less at time of transplant
6. Able and willing to conform to requirements of the study
7. Able and willing to provide informed consent or have legally authorized representative who is able and willing to provide informed consent

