## **Exclusion Criteria**

1.  $< 18$  years old
2. Autoimmune liver disease, Primary Sclerosing Cholangitis, Primary Biliary Cirrhosis
3. Dialysis greater than 45 days
4. Receiving ATG, IVIG therapy, or sirolimus/everolimus around time of transplant or sirolimus/everolimus after transplant
5. Unable to take oral medications at 1 month post transplant
6. Participating in another clinical research study involving the evaluation of another investigational drug or device
7. Documented allergy to basiliximab, TAC, MMF or any macrolide antibiotic.
8. Presence of thrombosis of any major hepatic arteries
9. Complex/high risk arterial reconstruction at any time (graft vessel patency by Doppler ultrasound confirmed and documented).
10. Patients who are recipients of multiple solid organ transplants, (e.g., multivisceral or combined liver-kidney transplants), or have previously received an organ or tissue transplanted, or who received an ABO incompatible transplant.
11. Patients who have severe hypercholesterolemia ( $>215$  mg/dL;  $>5.5$  mmol/L) or hypertriglyceridemia ( $>265$  mg/dL;  $>3.0$  mmol/L) at Baseline.
12. Patients who have severe thrombocytopenia or neutropenia (platelet count  $>20$  and MLCs $>1000$ )
13. Patients who have any surgical or medical condition, which in the opinion of the investigator, might significantly alter the absorption, distribution, metabolism and excretion of study drugs
14. Patients with a known hypersensitivity to the drugs used on study or their class, or to any of the excipients.
15. Patients with clinically significant systemic infection
16. Pregnant or nursing (lactating) female patients, where pregnancy is defined as the state of a female after conception and until the termination of gestation, confirmed by a positive  $\beta$ HCG laboratory test ( $>9$  mIU/mL) at Baseline.

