## DRUG THERAPY

### *Group 1*

#### Basiliximab

- Dose #1: 20mg IV within 2 hours of transplant
- Dose #2: 20mg IV Post-operative day #4

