#### Tacrolimus (with basiliximab induction)

- Beginning day #5 post-transplant or when SCr  $\leq$  1.8 mg/dl (subjects off dialysis) to six months: 0.03-0.1mg/kg q12h PO to maintain whole blood trough concentration of 4-6ng/mL

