#### Everolimus (delayed)

- Add by POD 30: 1 mg po bid and adjusted to maintain whole blood trough concentrations of 3-8 ng/ml.

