##### *Group 3 (control):*

#### Tacrolimus (without basiliximab induction)

- Beginning day #1 post-transplant to six months: 0.03-0.1mg/kg q12h PO to maintain whole blood trough concentration of 5-12ng/mL
- Six months to one year: maintain whole blood trough concentration of 5-10ng/mL

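### A check on oral intake one month after transplant removes patients who are already randomised and treated, and no analysis set keeps them in

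*Protocol*

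**What the plan says.** The rule appears three times in the protocol.

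- Inclusion Criteria at Baseline, item 2: "Patients who are able to take oral medication at 1 month post transplant".
- Exclusion Criteria, item 5: "Unable to take oral medications at 1 month post transplant".
- Permitted dose adjustments and interruptions of study treatment, under Everolimus, which gives the oral route as the reason and the consequence: "patients who are unable to take oral medications by 1 month post transplant will be excluded from the study". The removal is from the study, not only from everolimus.

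On timing, Study Population expects at least 90 patients who "will fulfill the inclusion and none of the exclusion criteria at baseline and will be able to be randomized in a 2:2:1 manner". The day of randomisation is not given. Under Drug Therapy, Groups 1 and 2 receive basiliximab ("Dose #1: 20mg IV within 2 hours of transplant") and start tacrolimus later ("Beginning day #5 post-transplant or when SCr" falls to a set threshold). Group 3 has no basiliximab and takes tacrolimus "Beginning day #1 post-transplant to six months". Everolimus is listed only in the Group 2 regimen, to be added by day 30.

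On follow-up, both Patient Population sections plan six months for every patient, and Criteria for Early Withdrawal extends this to those who discontinue the trial. None of them says whether a patient excluded at month 1 is covered. The list of reasons under Study treatment discontinuation does not mention inability to take oral medication.

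On analysis, the protocol's Statistical analysis section is still to be written. The SAP names tests, a two-sided 0.05 level and software, but no analysis population and no rule for missing outcomes.

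**The concern.** A condition that can be observed only a month after transplant cannot screen patients before randomisation. Applied as written, it works as a post-randomisation exclusion. By month 1 the patients concerned already have creatinine and eGFR at weeks 1, 2 and 4, and 1-month rejection and dialysis outcomes, all listed as secondary endpoints. Some may also have reached dialysis independence, part of the primary objective.

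If they are left out of the analysis, each arm's result describes a selected group. For comparisons with Group 3, selection occurs after the treatments have diverged, so the retained patients may no longer be comparable. The trial is open label, and the rule's only stated reason concerns a drug listed in one arm, so staff would apply it knowing the allocation. An analysis set can still be written later. Outcome data that were never collected cannot be recovered.

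**Working it through.** **Order of events.** Randomisation follows baseline eligibility (Study Population). Basiliximab is due within 2 hours of transplant in two arms and tacrolimus starts on day 1 in the third, so allocation must be known by about the time of transplant. The check falls at about day 30. It therefore follows both randomisation and the start of assigned treatment. This is inferred from the drug timings.

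**Which comparisons are exposed.** Against Group 3, the regimens differ from transplant, so the month-1 state arises after they diverge. The regimens listed for Groups 1 and 2 are the same until about day 30, so for that pair the state arises before they diverge.

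**The plan's own figure.** 90 × (2, 2, 1)/5 = 36, 36, 18. This reproduces exactly. The documents give no event rate, effect size or exclusion rate, so every input below is assumed.

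**Patients left if all who fail the check are dropped** (rounded within arm):

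| Unable | Groups 1 / 2 / 3 | Total | Range of Group 1 − Group 3 difference with nothing known about those dropped |
|---|---|---|---|
| 5% | 34 / 34 / 17 | 85 | 11.1 points |
| 10% | 32 / 32 / 16 | 80 | 22.2 points |
| 15% | 31 / 31 / 15 | 77 | 30.6 points |
| 20% | 29 / 29 / 14 | 72 | 41.7 points |

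The last column is the sum of the two excluded shares, for example 2/36 + 1/18 = 11.1 points.

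**Illustrations for dialysis independence.** This outcome is defined for everyone only if all patients were on dialysis before transplant, as the SAP title says. The protocol title is wider. Let u be the share unable (equal across arms), f the fraction of them excluded, and q their rate of dialysis independence (20% or 40%). The others have 80%.

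Observed rate = [(1 − u) × 0.80 + u(1 − f)q] / (1 − uf).

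- (a) Full exclusion in every arm, no true effect: the difference is 0, but each rate rises by u(0.80 − q).
- (b) Full exclusion in every arm, with a 20-point effect in retained patients (say 80% against 60%) and none in excluded patients: 20 points are seen, against (1 − u) × 20 in all randomised.
- (c) Full exclusion in one arm, half in another, no true effect. For u = 0.20 and q = 0.20, the second arm shows (0.64 + 0.02)/0.90 = 73.3% against 80.0%, a gap of 6.7 points.
- (d) Exclusion in one arm only, no true effect: the gap is u(0.80 − q).

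| u | (a) rise in every rate, and (d) false gap, q = 20% / 40% | (b) effect in all randomised | (c) false gap, q = 20% / 40% |
|---|---|---|---|
| 5% | 3.0 / 2.0 | 19 | 1.5 / 1.0 |
| 10% | 6.0 / 4.0 | 18 | 3.2 / 2.1 |
| 15% | 9.0 / 6.0 | 17 | 4.9 / 3.2 |
| 20% | 12.0 / 8.0 | 16 | 6.7 / 4.4 |

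- (e) The share unable itself differs by arm. Assume 80% independence among all patients in both arms and 30% among those unable. The retained rate is (0.80 − 0.30u)/(1 − u). With 5% unable in Group 1 and 15% in Group 3, this gives 0.785/0.95 = 82.6% and 0.755/0.85 = 88.8%, a false gap of 6.2 points. With 20% in Group 3 it is 0.74/0.80 = 92.5%, a gap of 9.9 points. With 10% in both arms it is 0.

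In (c), (d) and (e) the sign reverses if the arms are swapped.

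**The case against.** The strongest case on the other side has four parts.

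- **The regimens do not all differ from transplant.** This stands. For Group 1 versus Group 2, the pair that isolates everolimus, the exclusion acts much like restricting the comparison to patients in a given state at month 1. What remains is loss of patients, a narrower population and open-label application.
- **The numbers prove little.** This largely stands. All inputs are assumed. Case (a) gives no false difference, and case (b) is a change in the population described, not a false effect. Cases (c) and (d) need uneven application, which no passage directs. Case (e) needs the regimens to affect oral intake at one month, which no passage shows. One patient is 1/36 = 2.8 points in a large arm and 1/18 = 5.6 points in Group 3, so the 1 to 4 point shift in (b) is less than one control patient.
- **Follow-up is already promised.** This stands in part. Six months is planned for each patient and for those who discontinue. Loss of follow-up is possible because the word excluded is left open, but the text does not direct it.
- **The missing analysis set is a general gap.** This is true: it affects every route of discontinuation in a trial that calls itself a pilot. Here, however, there is also a stated rule that takes randomised patients out, so the point goes beyond missing detail.

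The rule might also be read as a forecast made at baseline. The Everolimus text ties exclusion to the state by one month, which cannot be known at baseline, so the wording would need correcting on that reading too.

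**Conclusion.** The point holds in limited form. Following the protocol as written removes randomised patients on a post-randomisation state, after they have contributed first-month data, and nothing in either document keeps them in the analysis. Treatment-related selection can bias Groups 1 and 2 against Group 3.

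A reader might infer more than this: that all three comparisons are biased alike, that the rule will be enforced only in Group 2, that follow-up will stop, or that results will be off by up to 12 points in a known direction. The documents support none of these. They give no size or direction. The figures of 1 to 12 points are illustrations that rest on 5 to 20% being unable, with 20 to 40% dialysis independence in those patients and 80% in the others (in case (e), 30% in those patients and 80% overall).

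Severity: should-fix. The conflict is real and cheap to remove, but the harm depends on how the rule is applied and on an analysis choice not yet stated.

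**What to change.** Reconcile six protocol sections: Study Population, Inclusion Criteria at Baseline, Exclusion Criteria, Everolimus (under permitted dose adjustments), Study treatment discontinuation, and Criteria for Early Withdrawal. Failing the month-1 oral-intake condition should not remove a randomised patient from the study or from the six-month follow-up already planned. Whether oral intake is a condition for starting everolimus is for the sponsor to decide.

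Add to the SAP:

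> All randomised patients who are transplanted are analysed in the arm assigned, including Group 2 patients who never start everolimus; randomised patients not transplanted are reported by arm with the reason and are not in this set. The number unable to take oral medication at 1 month is reported by arm.

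If any patients have already been excluded under this rule, report them by arm and include their available data.

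Cost: wording in six protocol sections, two SAP sentences, and submission of the modification to the IRB, which the protocol requires. No visits are added, since six months of follow-up is already planned for each patient. The downside is some dilution of the everolimus effect from Group 2 patients who never start it; in case (b), 20 points would read as 16 to 19. A rule for missing outcomes is still needed separately.

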### **Discontinuation of study treatment and premature patient withdrawal**

#### **Study treatment discontinuation**

The investigators will discontinue study medication for a given patient or withdraw the patient from study if, on balance, he/she believes that continuation would be detrimental to the patient's well-being. In the absence of medical contraindication or significant protocol violation, every effort will be made to continue the patient on study medication

Reasons for study drug discontinuation include:

- Death.
- Graft loss and/or re-transplantation.
- Pregnancy
- Withdrawal of consent.
- Emergence of any serious adverse event (at the discretion of the investigator).
- Unsatisfactory therapeutic effect (e.g. repeated acute rejection).
- Administration of prohibited immunosuppressive medication.
- Abnormal laboratory value(s) not resolved after study treatment interruption for more than 21 consecutive days or more than 2 episodes longer than 10 days, everolimus C-0h blood trough level  $\geq 3$  ng/mL cannot be maintained due to toxicity.
- Abnormal test procedure result(s).
- Significant protocol violation.
- Any other protocol deviation that results in a significant risk to the patient's safety.
- Lost to follow-up.

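### The protocol gives three unranked responses to an everolimus trough below 3 ng/mL after a dose cut for toxicity, and one of them can raise the dose above the one not tolerated

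*Protocol*

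**What the plan says.** Only Group 2 receives everolimus. The protocol starts it at 1 mg twice daily and targets a trough of 3-8 ng/mL (Introduction and maintenance of everolimus).

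The section Permitted dose adjustments and interruptions of study treatment is written for patients who cannot tolerate the regimen. Its Everolimus subsection lists falling blood counts, rising lipids and other adverse events as grounds for adjustment, and then gives these rules in this order:

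- **Size of a reduction:** "The everolimus dose should be decreased by at least one third of the total daily dose of the study if a dose reduction is necessary".
- **Floor after a reduction:** "The everolimus C-0h blood trough level should still be kept" at or above 3 ng/mL.
- **Stop:** everolimus is to be discontinued if that floor "cannot be maintained due to toxicity or intolerable side-effects".
- **Low trough:** below 3 ng/mL, "everolimus will be increased by doubling the dose".
- **High trough:** above 8 ng/mL, "the everolimus dose will be decreased by at least by 25 % of the daily dose".
- **Discretion:** interruptions and temporary troughs below 3 ng/mL "are up to the discretion of the investigator and the investigator has to assure for adequate immunosuppression". A temporary rise in tacrolimus exposure is given as the way to do this.

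Study treatment discontinuation repeats the stop rule. The list entry that begins "Abnormal laboratory value(s) not resolved after study treatment interruption for more than 21 consecutive days" ends by naming a trough of at least 3 ng/mL that cannot be held because of toxicity.

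The Safety objectives include the incidence of, and reason for, dose interruption, dose adjustment and premature discontinuation of study medication.

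**The concern.** Take a Group 2 patient whose everolimus is cut by one third for falling platelets and whose next trough is below 3 ng/mL. The protocol offers three actions: double the dose, stop the drug, or accept the low trough for a time and raise tacrolimus. It does not rank them. The doubling sentence makes no exception for a dose that was lowered for toxicity, and nothing says how long a low trough may last and still be temporary.

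Two things are at stake. The first is safety: one of the three actions, applied as written, can give the patient more drug than the dose that was not tolerated. The second is what the safety data would mean. The same clinical situation could be counted as a dose increase, a tolerated low trough or a discontinuation, depending on which sentence the treating clinician followed. The counts under Safety objectives would then partly reflect that choice rather than tolerability.

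**Working it through.** The plan states no figure on this point, so there is none to reproduce. The check has three parts.

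**1. The sentences side by side**, for a trough below 3 ng/mL after a toxicity cut:

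| Sentence | Condition | Action | Excludes the other two? |
|---|---|---|---|
| Low trough | trough below 3 ng/mL | double | no |
| Stop | 3 ng/mL or more cannot be held because of toxicity | discontinue | no |
| Discretion | trough temporarily below 3 ng/mL (duration undefined) | investigator decides; more tacrolimus | no |

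A single patient can meet all three conditions. The discontinuation list repeats the second row but does not rank it against the others.

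**2. Dose arithmetic.** Let the earlier dose be D and the cut a fraction r, where the protocol requires r of at least 1/3 and sets no upper limit. After the cut the dose is (1 − r)D. After doubling it is 2(1 − r)D, which exceeds D only if r is below 1/2. With D = 2 mg/day (1 mg twice daily):

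| Cut r | Dose after cut (mg/day) | Dose after doubling (mg/day) | Relative to D |
|---|---|---|---|
| 1/3 | 1.33 | 2.67 | 1.33 |
| 0.40 | 1.20 | 2.40 | 1.20 |
| 1/2 | 1.00 | 2.00 | 1.00 |
| 0.60 | 0.80 | 1.60 | 0.80 |
| 2/3 | 0.67 | 1.33 | 0.67 |

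The doubled dose is therefore higher than the dose not tolerated for cuts from one third up to, but not including, one half. It is equal at one half and lower beyond that.

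**3. When the low-trough sentence comes into play.** This step assumes that trough is proportional to dose, which the documents do not state. A cut r takes a prior trough T below 3 ng/mL if (1 − r)T < 3, that is, if T < 3/(1 − r).

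- r = 1/3: T < 4.5 ng/mL
- r = 0.40: T < 5.0 ng/mL
- r = 1/2: T < 6.0 ng/mL

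For the minimum cut, in-range prior troughs of 3 to under 4.5 ng/mL are affected. This is (4.5 − 3)/(8 − 3) = 30% of the width of the target range. Doubling would then give 4/3 of the prior trough, so 4 to under 6 ng/mL. The 30% is a share of the range and not of patients, because the documents give no distribution of troughs.

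**The case against.** The strongest reply is that the text can be read sensibly as it stands. On that reading, the opening sentences set out a toxicity path: reduce, hold 3 ng/mL, otherwise stop. The doubling and 25% sentences are then routine trough titration, and the last sentence covers short dips. The section is introduced as guidelines, and the discontinuation section lets the investigator stop whenever continuing would be detrimental. Even after doubling, the trough in the worked case (4 to under 6 ng/mL) lies within the 3-8 target.

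Much of this stands. A reader might infer that doubling is compulsory after a toxicity cut. The documents do not support that, because stopping and discretion are offered for the same trough. A reader might also infer that doubling always overshoots the earlier dose, but it does so only for cuts below one half.

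Nor do the one-third and 25% minimum steps truly conflict. The 25% step is tied to troughs above 8 ng/mL, the one-third step follows the sentence on intolerance, and a cut of one third also satisfies the 25% minimum. Finally, no case report form is among the documents, so it cannot be said that the reason for each dose change goes unrecorded.

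What does not stand is the claim that the text itself supplies the sensible reading. The doubling sentence sits in a section for patients who cannot tolerate the regimen, follows directly on the toxicity sentences, and carries no exception. The protocol never says that it is confined to routine titration.

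**Conclusion.** The concern holds as a narrow internal inconsistency with a safety consequence. Three responses to a trough below 3 ng/mL after a toxicity cut stand together without precedence, and neither the introduction to the section nor the discontinuation list resolves them.

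In size, doubling after the minimum cut gives 4/3 of the dose not tolerated. This follows from the protocol's own step sizes and needs no pharmacokinetic assumption. It is confined to cuts from one third to under one half that take the trough below 3 ng/mL. The band of affected prior troughs (3 to under 4.5 ng/mL for a one-third cut) does rest on assumed proportionality.

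The number of patients cannot be estimated. It is bounded by the 36 planned for Group 2, and within them by those who need a toxicity cut and then have a low trough. A reader might infer that centres would diverge, but this is a single-center trial. The possible variation is between clinicians, or between occasions, and it carries through to the counts of dose adjustment, interruption and discontinuation.

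**What to change.** The sponsor should reconcile the sentences of the Everolimus subsection with each other and with Study treatment discontinuation. The amended text should state which sentence governs a trough below 3 ng/mL that follows a reduction made for toxicity, and what counts as temporary. Which rule is clinically right is for the sponsor and investigator to decide, and none is proposed here.

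The cost is a short protocol amendment, with no extra patients, visits or tests. While making it, the sponsor should confirm that the data collected separate dose changes made for toxicity from those made for a trough value, so that the counts under Safety objectives can be interpreted.
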